6. GENERAL CONSIDERATIONS

Data will be summarised descriptively (frequency and percentage for categorical data and mean and standard deviation [SD] for continuous data, unless specified otherwise). In summary tables for categorical data for which categories are defined on the electronic case report form (eCRF), all categories will be presented as specified, even if the subject count within that category is zero.

Unless otherwise specified, all data collected during the trial will be presented in listings.

Document : \quintiles.net\enterprise\Apps\sasdata\SASb\SAS\GSK\Infanrix\PPD \Biostatistics\Documentation\NSAP

Author: PPD Version Number: 1.0

Version Date: [07JAN2021]

Template No.: CS_TP_BS016 Revision 6

Reference: CS_WI_BS005

Effective Date: 02Dec2019

6.1. REFERENCE START DATE AND STUDY DAY

Study Day will be calculated from the reference start date and will be used to show start/stop day of assessments and events.

Reference start date is defined as the day of the first dose of study treatment, (Day 1 is the day of the first dose of study treatment).

- If the date of the event is on or after the reference date, then:

$$\text{Study Day} = (\text{date of event} - \text{reference start date}) + 1.$$

- If the date of the event is prior to the reference date, then:

$$\text{Study Day} = (\text{date of event} - \text{reference start date}).$$

In the situation where the event date is partial or missing, Study Day and any corresponding durations will appear partial or missing in the listings. Refer to [Appendix 2](#) for partial date conventions.

6.2. WINDOWING CONVENTIONS

The following table describes assignment of visit windows for two reasons:

- Vaccination and blood draw intervals for purposes of analysis.
- If a subject has fever (temperature $\geq 38^{\circ}\text{C}$), the vaccination should be postponed, and a new visit will be scheduled.

Table C: Intervals between Study Visits

Interval	Length of interval	Allowed interval
Birth (age is 0 day on birth date) \rightarrow Visit 1	6 to 12 weeks	42 to 84 days
Visit 1 \rightarrow Visit 2	60 days	52 to 78 days
Visit 2 \rightarrow Visit 3	30 days	21 to 48 days
Birth \rightarrow Visit 4	365 days	335 to 395 days
Visit 4 \rightarrow Visit 5	30 days	21 to 48 days

Document: \quintiles.net\enterprise\Apps\sasdata\SASb\SAS\GSK\Infanrix\PPD\Biostatistics\Documentation\NSAP

Author: PPD Version Number: 1.0

Version Date: [07JAN2021]

Template No.: CS_TP_BS016 Revision 6

Reference: CS_WI_BS005

Effective Date: 02Dec2019

Interval is computed as the difference between the 2 dates meaning that visit 2 should be on or between Day 53 and Day 79. In other words, a subject with dose 2 vaccination on January 1 will be eliminated if the blood draw is on January 21 but will not be eliminated if the blood draw is on January 22.

6.3. STATISTICAL TESTS

The default confidence interval level will be 2 sided 95% with equal tail, unless otherwise specified in the description of the analyses.

6.4. COMMON CALCULATIONS

Geometric Mean Concentration (GMC)

Distributions of antibodies are generally skewed to the right ([Nauta, 2010](#)). Therefore, prior to any statistical analysis that assumes normally distributed observations, antibody titers or concentrations will be log10-transformed. GMCs and their 95% CIs are computed by exponentiating (base 10) the least squares mean and 95% CIs of the log10 titers.

The GMC will be calculated using the following formula:

$$10^{\left(\frac{\sum_{i=1}^n \log 10(t_i)}{n}\right)}$$

Where t_1, t_2, \dots, t_n are n observed immunogenicity titers/concentrations.

Concentration below assay cut-off (i.e., <lower limit of quantitation or < LLOQ) will be replaced by half the assay cut-off (LLOQ/2) for the purpose of GMC computation.

6.5. SOFTWARE VERSION

All analyses will be conducted using SAS version 9.4 or higher.

Document : \quintiles.net\enterprise\Apps\sasdata\SASb\SAS\GSK\Infanrix\PPD \Biostatistics\Documentation\n\SAP

Author: PPD Version Number: 1.0

Version Date: [07JAN2021]

Template No.: CS_TP_BS016 Revision 6

Reference: CS_WI_BS005

Effective Date: 02Dec2019

7. STATISTICAL CONSIDERATIONS

7.1. ADJUSTMENTS FOR COVARIATES AND FACTORS TO BE INCLUDED IN ANALYSES

The following factors will be used in the analyses. For details, refer to Section 16.1 and 16.2. The model will include country, maternal immunisation and treatment group as fixed categorical effects in the Analysis of Variance (ANOVA) model.

7.2. MULTICENTER STUDIES

This study will be conducted by multiple investigators at multiple centres in 3 European countries. The subjects will be randomised at a 1:1 ratio to Inv_group or Com_group using a minimisation algorithm with the study country and maternal immunisation status as minimisation factors.

Descriptive immunogenicity analysis will be performed by country (refer to section 7.5). Country will be pooled for safety and inferential analysis. Additional analyses by country will be conducted as deemed necessary as per Section 7.5.

7.3. MISSING DATA

Missing data (missing, incomplete or partial dates, AE measurement (including missing AE severity and relationship), prior and concomitant medications and death date) will be handled as per [Appendix 2](#) of this analysis plan.

Missing immunogenicity data will not be imputed. Concentration below assay cut-off (i.e., lower limit of quantitation or < LLOQ) will be replaced by half the assay cut-off (LLOQ/2) for the purpose of GMC computation.

CCI

[REDACTED]

CCI

[REDACTED]

Document : \quintiles.net\enterprise\Apps\sasdata\SASb\SAS\GSK\Infanrix\PPD \Biostatistics\Documentation\n\SAP

Author: PPD Version Number: 1.0

Version Date: [07JAN2021]

Template No.: CS_TP_BS016 Revision 6

Reference: CS_WI_BS005

Effective Date: 02Dec2019

CCI

7.4. ACTIVE-CONTROL STUDIES INTENDED TO SHOW NON-INFERIORITY OR SUPERIORITY

Non-inferiority will be demonstrated in terms of an endpoint if:

- 1. The lower limit of 2-sided 95% confidence interval (CI) on group GMC ratio (Inv_group over Com_group) from the ANOVA model is above 0.5.
- 2. The lower limit of the 2-sided 95% CI on group difference in the percentage (inv_group minus Com_group) is above -10%.

Superiority will be demonstrated in terms of an endpoint if:

- 3. The lower limit of 2-sided 95% confidence interval (CI) on group GMC ratio (Inv_group over Com_group) from the ANOVA model is above 1.
- 4. The lower limit of the 2-sided 95% CI on group difference in the percentage (Inv_group minus Com_group) is above 0.

For each objective, concluding is only possible if the previous objective(s) (ie 1, 2, 3 as shown above) in the hierarchy has been reached

Additional details provided in Section 16.1.

7.5. EXAMINATION OF SUBGROUPS

Descriptive summaries of immunogenicity analyses will be performed by country and by maternal immunization status, respectively unless a subgroup covers less than 50 subjects in the PPS at one month post booster dose or more than the total number of subjects in the PPS minus 50 at one month post booster dose.

8. OUTPUT PRESENTATIONS

APPENDIX 1 shows conventions for presentation of data in outputs.

The templates that will be provided with this SAP describe the presentations for this study and therefore the format

Document : \quintiles.net\enterprise\Apps\sasdata\SASb\SAS\GSK\Infanrix\PPD \Biostatistics\Documentation\NSAP

Author: PPD Version Number: 1.0

Version Date: [07JAN2021]

Template No.: CS_TP_BS016 Revision 6

Reference: CS_WI_BS005

Effective Date: 02Dec2019

and content of the summary tables, figures, and listings to be provided by IQVIA Biostatistics. Statistical output numbering will follow 'ICH E3 Structure and Content of Clinical Study Reports'.

9. DISPOSITION AND WITHDRAWALS

All subjects who are enrolled in the study (those with a study intervention either randomised or vaccinated or with a blood draw) will be accounted for in this study.

9.1. DISPOSITION

Subject disposition, withdrawals, and reasons for exclusion from each analysis set, including inclusion as well as exclusion criteria will be presented for the ENR set. Specifically, the number of subjects, treated and completed the study will be summarized by study arm for the ENR set. Additionally, the number of subjects returning for each visit, discontinuing treatment but who continued further study procedures, discontinuing the study and the reason for discontinuation will be presented.

A listing of the disposition for all subjects with early withdrawal or discontinuation due to having COVID-19 or COVID-19 related issues information will be provided.

9.2. PROTOCOL DEVIATIONS

- Protocol deviations (PDs) will be collected in a PD log, as detailed in the Protocol Deviations Management Plan (PDMP).
- All PDs will be assessed as important and non-important. Protocol deviations will be reviewed by the sponsor, and their status confirmed by the time that all data are cleaned for the Final Analysis.
- A summary table presenting the frequency and percentage of subjects with important PDs will be presented for subjects in the ENR set.
- A listing of all PDs including an indicator of those excluded from the PPS and an indicator of COVID causality will be provided.

9.2.1. PROTOCOL DEVIATIONS RELATED TO STUDY CONDUCT

A PD is any noncompliance with the clinical trial protocol, good clinical practice (GCP), or Manual of Procedure

Document : \quintiles.net\enterprise\Apps\sasdata\SASb\SAS\GSK\Infanrix\PPD\Biostatistics\Documentation\NSAP

Author: PPD Version Number: 1.0

Version Date: [07JAN2021]

Template No.: CS_TP_BS016 Revision 6 Reference: CS_WI_BS005

Effective Date: 02Dec2019

requirements. The noncompliance may be either on the part of the subject, the site PI, the study site staff or the sponsor.

9.2.2. PROTOCOL DEVIATIONS RELATED TO IMMUNOGENICITY ANALYSIS

Changes to the procedures or events, which may impact the quality of the immunogenicity data, will be considered significant PDs and will be described within the clinical study report (CSR). This includes any circumstances that could alter the evaluation of the immunogenicity results such as sample processing errors that lead to inaccurate immunogenicity results, and/or inaccurate dosing which could exclude them from the PPS. In addition, subjects may also be eliminated from the PPS based on usage of certain concomitant medications or vaccines as described in Section 5.2.2 of the original Protocol version 1 dated 21 Feb 2020.

10. DEMOGRAPHIC AND OTHER BASELINE CHARACTERISTICS

Demographic data and other baseline characteristics will be presented for the ENR, ES and PPS analysis sets. The following demographic and other baseline characteristics will be reported for this study:

- Age (weeks) – at the time of first vaccination
- Gestational age (weeks)
- Sex
- Race (as per CDISC categories)
- Country
- Weight (kg)
- Height (cm) at Day 1
- Maternal immunisation status

Descriptive statistics (mean, median and standard deviation) will be presented for continuous variables and frequency counts and percentages for categorical variables. No statistical testing will be carried out for demographic or other baseline characteristics.

10.1. DERIVATIONS

- Age (weeks) at first vaccination = int ((Date of first vaccination – Date of birth + 1) / 7)
- Partial dates will be handled as per the rules in [Appendix 2](#).

Document : \quintiles.net\enterprise\Apps\sasdata\SASb\SAS\GSK\Infanrix\PPD \Biostatistics\Documentation
n\SAP

Author: PPD Version Number: 1.0

Version Date: [07JAN2021]

Template No.: CS_TP_BS016 Revision 6

Reference: CS_WI_BS005

Effective Date: 02Dec2019

11. COVID -19 CORONAVIRUS INFECTION ASSESSMENT AND DIAGNOSIS

The COVID-19 infection assessment and diagnosis data including assessment, symptom, level of care and diagnosis data will be presented for the ES and captured on the “COVID-19 Coronavirus Infection Assessment and Diagnosis” page of the eCRF.

A listing of this data will be provided.

12. GENERAL MEDICAL HISTORY AND EXAMINATIONS

Medical History and Examination information will be presented for the ENR.

- Medical History will be coded using Medical Dictionary for Regulatory Activities (MedDRA) central coding dictionary, Version 23.0 or higher.
- Data captured on the “General Medical History” page of the eCRF will be presented by SOC (System Organ Class) and PT (Preferred Term). Medical occurrences that begin before the start of study treatment but after obtaining informed consent will be recorded on the Medical History/Current Medical Conditions section of the eCRF, not the AE section.

In addition, if a medical disorder, allergy or surgery may be relevant to a SAE (Serious Adverse Event), this information will be recorded under the “Relevant Medical Condition(s)/ Risk Factor(s)” section of the “Expedited Adverse Events” page of the eCRF.

A listing of medical history data will be provided.

13. PRIOR, CONCOMITANT AND CO-ADMINISTERED VACCINATIONS

Prior, concomitant and co-administered vaccination will be coded with the GSK drug dictionary summarized by ingredient for the ES.

- Prior vaccinations are vaccinations given to subjects prior to the first dose of study treatment and are recorded on the eCRF.

Document : \quintiles.net\enterprise\Apps\sasdata\SASb\SAS\GSK\Infanrix\PPD \Biostatistics\Documentation\NSAP

Author: PPD Version Number: 1.0
Version Date: [07JAN2021]

Template No.: CS_TP_BS016 Revision 6

Reference: CS_WI_BS005

Effective Date: 02Dec2019

- *Prevenar 13* is co-administered with both *Infanrix hexa* and *Vaxelis* in this study as vaccination with a pneumococcal conjugate vaccine is part of the national recommendations in Europe.
- Concomitant vaccinations are defined as any vaccine that the subject is receiving as of the time of enrolment or receives during the study, other than study vaccine(s) as recorded on the “Concomitant Vaccination” page of the eCRF.

Co-administered vaccinations will be summarized for each dose while prior/concomitant vaccinations will be summarized by period:

- Before Dose 1
- Between Dose 1 & Dose 2 (this will include the concomitant vaccinations which took place after dose 1 when dose 2 was not given)
- Between Dose 2 & Visit 3 (this will include the concomitant vaccinations which took place between Dose 2 & booster dose when visit 3 is missing; this will include the concomitant vaccinations which took place after Dose 2 for subject who dropped out between Dose 2 and Visit 3)
- Between Visit 3 and booster dose (this will include the concomitant vaccinations which took place after visit 3 for subject who dropped out between Visit 3 and booster dose).
- After booster dose

Further details are in Section 5.2.2 of the Protocol.

In addition, if a concomitant vaccination may help explain an AE/SAE, the cause of the AE/SAE or the treatment of an AE/SAE, this information will be recorded under the “Relevant Concomitant/Treatment Medications/Vaccinations Entry” section of the “Expedited Adverse Events” page of the eCRF.

Data will be presented in tables summaries and listings.

14. MEDICATIONS

The percentage of subjects who started medications after Dose 1 will be presented by treatment group for the ES. The percentage of subjects who started medications with antipyretic action for any reason and for prophylactic reason will also be summarized. The antipyretic action will be derived from the anatomical therapeutic chemical (ATC) coding as per the latest version of the GSK drug dictionary.

See APPENDIX 2 for handling of partial dates for medications, in the case where it is not possible to define a

Document : \quintiles.net\enterprise\Apps\sasdata\SASb\SAS\GSK\Infanrix\PPD\Biostatistics\Documentation\NSAP

Author: PPD Version Number: 1.0

Version Date: [07JAN2021]

Template No.: CS_TP_BS016 Revision 6

Reference: CS_WI_BS005

Effective Date: 02Dec2019

medication as prior or after dose 1, the medication will be classified by the worst case; i.e. after dose 1.

- ‘Prior’ medications are medications which started prior to the first dose of study treatment.
- ‘Concomitant’ medications are any other medications which are received during the study as recorded on the “Medication” page of the eCRF (ended on or after the date of first dose of study medication or were ongoing at the end of the study)

Further details are in Section 5.2.2 of the Protocol.

15. STUDY TREATMENT EXPOSURE AND COMPLIANCE

Study treatment exposure will be presented for the ES. The distribution of the total number of *Infanrix hexa/ Vaxelis* doses will be summarized for the ES. The prescribed dosage, timing, and mode of administration may not be changed with any departures from the intended regimen recorded on the “Study Vaccine / Product Administration” page of the eCRF. For dosing instructions and route, refer to Table 3 on page 24 of the original Protocol version 1 dated 21 Feb 2020.

Compliance to study treatment will be presented for the ES. The frequency and percentage of subjects receiving 1 dose, 2 doses or all 3 doses will be presented overall and by treatment group.

Data will be presented in tables summaries and listings.

16. IMMUNOGENICITY OUTCOMES

16.1. PRIMARY IMMUNOGENICITY

16.1.1. PRIMARY IMMUNOGENICITY VARIABLE(S) & DERIVATION(S)

The primary immunogenicity objective to demonstrate that the Hib response in the investigational group is non-inferior to the Comparator group at 1-month post-booster vaccination will be based on the PPS. The primary immunogenicity objective to demonstrate that the Hib response in the investigational group is superior to the Comparator group at 1-month post-booster vaccination will be based on the ES.

Document : \quintiles.net\enterprise\Apps\sasdata\SASb\SAS\GSK\Infanrix\PPD \Biostatistics\Documentation
n\SAP

Author: PPD Version Number: 1.0
Version Date: [07JAN2021]

Template No.: CS_TP_BS016 Revision 6 Reference: CS_WI_BS005

Effective Date: 02Dec2019

16.1.2. MISSING DATA METHODS FOR PRIMARY IMMUNOGENICITY VARIABLE(S)

Missing data will not be replaced. Refer to Section 7.3.

16.1.3. PRIMARY ANALYSIS OF PRIMARY IMMUNOGENICITY VARIABLE(S)

In order to assess non-inferiority and superiority, the associated co-primary endpoints are assessed:

- anti-PRP antibody concentrations at 1-month post-booster vaccination
- anti-PRP antibody concentrations $\geq 5.0 \mu\text{g/mL}$ at 1-month post-booster vaccination

They are assessed in terms of:

- An adjusted GMC and GMC ratio with 2-sided 95% CI for treatment group which is derived from an ANOVA model on log10 transformed concentration will be tabulated for anti-PRP antibody concentrations. The model will include country, maternal immunisation and group as fixed effects. The Lower limit (LL) of the 2-sided 95% confidence interval (CI) on group GMC ratio (Inv_group over Com_group) will be calculated by exponentiating (base10) the least squares means and the lower and upper limits of the 95% CIs of the log transformed titers (base10) obtained from an ANOVA with factors for vaccine group, maternal immunisation and country.
- Percentage of subjects with anti-PRP antibody concentration $\geq 5.0 \mu\text{g/mL}$ at 1-month post-booster vaccination using 2-sided 95% CI on group difference in the percentage/seroconversion rate (Inv_group minus Com_group) computed based on Miettinen and Nurminen method [[Miettinen](#), 1985].

Refer to Section 2.1 for the criteria used to make conclusions.

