### **6.4.3 Intervention Allocation to the Subject**

Treatment allocation: The subjects will be randomised in a 1:1 ratio to either the Inv\_group or Com\_group ([Section 1.2](#) and [Section 6.1](#)) using a minimisation algorithm with the study country and maternal immunisation as minimisation factors. This will be done at study entry, i.e., on Day 1 after consent was obtained and subjects were determined to be eligible, using IVRS randomisation.

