## 9.2 Sample Size Determination

The study will enrol approximately 500 subjects in a 1:1 ratio. Assuming that 20% of the subjects would not be evaluable, the power was computed for 400 evaluable subjects (i.e., 200 subjects each in the Inv\_group and Com\_group). Evaluable is defined as: meeting all eligibility criteria, complying with the procedures defined in the protocol, and, therefore, qualified for inclusion in the according-to-protocol analysis.

A 2.5% nominal type I error was used for each co-primary evaluation. To control the overall type I error below 2.5%, a hierarchical procedure will be used for the multiple study objectives. The study has:

- More than 99% power to reach the first co-primary objective. This power is obtained from PASS 2012, 1-sided t-test (non-inferiority with 0.5 group ratio as margin, i.e., -0.301 in  $\log_{10}$  Scale) for 2 independent means with common 0.63 variance of  $\log_{10}$  transformed anti-PRP concentration, under the specific alternative that the group GMC ratio is 1.75 [Silfverdal, 2016], i.e., 0.2430 in  $\log_{10}$  scale, and
- More than 99% power to reach the second co-primary objective. This power is obtained from PASS 2012, 1-sided Miettinen and Nurminen [Miettinen, 1985] test (non-inferiority with -10% margin) for 2 independent proportions under the specific alternative that the proportions are 46% after *Vaxelis* and 62% after *Infanrix hexa* [Silfverdal, 2016] while accounting for the power to meet the first co-primary objective.
- Approximately 97% power to reach the third co-primary objective. This power is obtained from PASS 2012, 1-sided t-test (inequality) for 2 independent means with common 0.63 variance in  $\log_{10}$  scale, under the specific alternative that the group GMC ratio is 1.75 [Silfverdal, 2016], i.e., 0.2430 in  $\log_{10}$  scale while accounting for the power to meet the first co-primary objective.
- At least 80% power to reach all co-primary objectives. This power is obtained from PASS 2012, 1-sided Z test (inequality) with pooled variance for 2 independent proportions under the specific alternative that the proportions are 46% after *Vaxelis* and 62% after *Infanrix hexa* [Silfverdal, 2016] while accounting for the power to meet the first 3 co-primary objectives.

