### 9.4.3 Immunogenicity Analyses

The confirmatory analyses of non-inferiority will be based on the PPS while the confirmatory analyses of superiority will be based on the ES.

- Method for non-inferiority and superiority in anti-PRP antibody concentration at 1-month post-booster vaccination:

- The 2-sided 95% CI for group GMC ratio derived from an ANOVA model on  $\log_{10}$  transformed concentration will be used. The model will include country, maternal immunisation and group as fixed effects. (Missing data will not be replaced. Concentration below assay cut-off will be replaced by half the assay cut-off).
- Method for non-inferiority and superiority in the percentage of subjects with anti-PRP antibody concentration  $\geq 5.0 \mu\text{g/mL}$  at 1-month post-booster vaccination:
  - The 2-sided 95% CI on group difference in seroconversion rate (Inv\_group minus Com\_group) will be computed based on Miettinen and Nurminen method [[Miettinen, 1985](#)].
- Descriptive analysis for each study group will be provided by country for Anti-PRP antibody concentrations at 1-month post-primary vaccination, pre-booster and 1-month post-booster vaccination, and for the percentage of subjects with anti-PRP antibody concentration  $\geq 5.0 \mu\text{g/mL}$  at 1-month post-booster vaccination.

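### The confirmatory interval for the percentage at or above 5 µg/mL could be stratified by the two allocation factors: an optional improvement worth at most about 2.6 power points, not an error

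*SAP*

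**What the plan says.** **Allocation.** Protocol 6.4.3 randomises 1:1 "using a minimisation algorithm with the study country and maternal immunisation as minimisation factors". SAP 7.2 repeats this.

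**GMC endpoint.** Protocol 9.4.3 and SAP 16.1.3 use an ANOVA on log10 concentrations: "The model will include country, maternal immunisation and group as fixed effects".

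**Percentage endpoint.** The interval in Protocol 9.4.3 "will be computed based on Miettinen and Nurminen method". SAP 16.1.3 gives the same method: "using 2-sided 95% CI on group difference in the percentage/seroconversion rate (Inv_group minus Com_group) computed based on Miettinen and Nurminen method". Neither names strata or weights.

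**Scope of the factors.** SAP 7.1 refers to both 16.1 and 16.2 but then assigns the factors to one model only: "The model will include country, maternal immunisation and treatment group as fixed categorical effects in the Analysis of Variance (ANOVA) model". SAP 7.2 adds: "Country will be pooled for safety and inferential analysis".

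**Analysis sets and sizing.** Non-inferiority uses the PPS, "while the confirmatory analyses of superiority will be based on the ES". Protocol 9.2 sizes superiority on the percentage with an unstratified pooled Z test at 46% versus 62% and 200 evaluable subjects per group. It claims "At least 80% power to reach all co-primary objectives".

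**The concern.** Both co-primary endpoints derive from the same anti-PRP concentration, yet only one is analysed with the factors used in allocation, and no reason is given. Minimisation balances those factors between groups. If they predict response, the true sampling variance of the difference is smaller than the unstratified formula assumes. The interval is then too wide and the test conservative.

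What is at stake is a small amount of power for superiority on the percentage. That is the fourth and last step of the hierarchy, called objective 4 below.

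**Working it through.** **Inputs from the documents.** One-sided 2.5% per objective; 46% and 62%; 500 enrolled with 20% not evaluable, so 400 evaluable and 200 per group (Protocol 9.2). The ES cannot exceed 500/2 = 250 per group.

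**Inputs assumed.** Three countries in proportions 40/35/25%, with maternal immunisation 50/50 (the balanced mix). Effects are set on a latent normal scale with SD 1: country shifts of 0, ±0.2, ±0.3 or ±0.5, and a maternal difference of 0, 0.3, 0.5 or 0.5. These are called none, mild, moderate and strong.

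**The plan's own figure.** Objective 4 alone, pooled Z, 200 per group:
- null SE = √(2 × 0.54 × 0.46 / 200) = 0.04984
- alternative SE = √((0.46 × 0.54 + 0.62 × 0.38) / 200) = 0.04919
- power = Φ((0.16 − 1.96 × 0.04984) / 0.04919) = Φ(1.267) = 89.7%

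The same formula gives 92.8% at 225 and 95.1% at 250 per group. With 97.0% for GMC superiority (reproduced when 0.63 is taken as an SD) and 99.96% for non-inferiority on the percentage, the product is 0.9705 × 0.9996 × 0.8974 = about 87%. This is consistent with the stated floor of 80%.

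**Tests compared.** A lower limit above 0 is equivalent to z > 1.96. In stratum k, let d be the difference in proportions, p the pooled proportion and N = n1 + n0. Then

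z = Σ w·d / √(Σ w²·v), with w = n1·n0/N and v = p(1 − p)(1/n1 + 1/n0)·N/(N − 1).

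The unstratified test is the one-stratum case.

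**Simulation.** 40,000 trials per scenario; 500 subjects; biased-coin minimisation on the two factor margins; 80, 90 or 100% with a result; sparse cells merged. All entries are percentages, unstratified → stratified. The null is 46% in both groups (Monte Carlo SE 0.08).

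| Effect (comparator stratum rates) | One-sided error, 200/group | Power, 200/group | Power, 225/group | Power, 250/group |
|---|---|---|---|---|
| None (46%) | 2.54 → 2.56 | 89.7 → 89.6 | 92.7 → 92.6 | 95.4 → 95.0 |
| Mild (33–61%) | 2.52 → 2.62 | 90.1 → 90.5 | 93.1 → 93.4 | 95.5 → 95.5 |
| Moderate (26–70%) | 2.23 → 2.58 | 90.5 → 91.7 | 93.6 → 94.5 | 96.0 → 96.3 |
| Strong (19–79%) | 1.87 → 2.61 | 90.9 → 93.5 | 94.2 → 96.0 | 96.6 → 97.5 |

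**Mechanism check.** The stratified-to-unstratified SE ratio was 0.965 (moderate) and 0.930 (strong). The implied unstratified error is Φ(−1.96/0.965) = 2.1% and Φ(−1.96/0.930) = 1.75%, close to the simulated 2.23% and 1.87%.

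**Sensitivity.**
- Sparse mixes (smallest country 10% or 4%, maternal immunisation 15%), 200 per group: −0.1 to 0 (none), +0.1 to +0.2 (mild), +0.7 to +0.8 (moderate), +1.3 to +1.6 (strong). Merging occurred in 96.5 to 100% of trials.
- Maternal effect in one vaccine group only: +0.9 (moderate) and +2.0 (strong). Opposite maternal effects in the two groups, no country effect: −0.1.
- A separate simulation with a logistic response model gave −0.3 (none) to +2.4 points (strong, rates 16–79%). Unstratified error fell to 1.67% and stratified error was 2.54% in that strong case.

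**Other objectives.** Power for non-inferiority on the percentage is at least 99.9% with either interval. All four objectives together, simulated on correlated endpoints at 200 per group: 88.9–91.1% unstratified and 88.8–93.5% stratified if 0.63 is an SD; 82.9–87.9% and 82.7–89.8% if it is a variance, as Protocol 9.2 labels it. Under the variance reading a simple product gives about 77%, but it treats tests on the same concentrations as independent.

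**The case against.** The strongest reply is that nothing is broken. Sizing and analysis of objective 4 are both unstratified, so they match. Minimising on a factor does not oblige every analysis to stratify by it. The sign of the gain is unknown, because the documents give no country mix, maternal immunisation prevalence or prognostic strength. Objective 4 is tested on the ES, which should usually hold more than 200 per group with results because it keeps subjects excluded from the PPS for deviations, so the 200-per-group gains lean high. With sparse cells, merging would drop maternal immunisation from some strata. A rule applied separately to each set could give the PPS and ES different strata. The change also touches a confirmatory analysis and needs formal documentation.

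Most of this stands and limits the point to an optional improvement. It does not remove it: the error rate is conservative if the factors matter, the remedy is standard, and the possible loss is smaller than the possible gain. The differing-strata problem is real, and the fix below closes it.

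A reader might also infer that SAP 7.2 contradicts the country term in the ANOVA, or would contradict a stratified interval. It does not. Read after the sentence on descriptive results by country, the pooling statement means one overall inference rather than country-by-country inference. Both an adjusted GMC ratio and a stratified difference provide that.

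**Conclusion.** The point holds as a low-cost improvement to a valid plan. If country and maternal immunisation are prognostic, the unstratified superiority test on the percentage runs at about 1.7 to 2.3% one-sided error under moderate to strong assumed effects, and stratifying brings it back to about 2.5%.

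The change in objective 4 power at 200 per group with a balanced mix is about 0, +0.4, +1.2 and +2 to +2.6 points for no, mild, moderate and strong effects. It is smaller with sparse mixes. At 250 per group it is at most about +0.9. If the factors are not prognostic, up to about 0.4 points are lost. All of these rest on assumed stratum sizes and effects.

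Two stronger readings are not supported. A reader might infer that ignoring the minimisation factors inflates type I error or invalidates the conclusion; any material departure from 2.5% is in the conservative direction. A reader might also take the upper end of the gain as the expected benefit; it needs comparator rates ranging from 19 to 79% across strata and only 200 per group in the ES, and the documents establish neither.

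**What to change.** Before unblinding:

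1. **Protocol 9.4.3 and SAP 16.1.3.** Specify the 95% Miettinen-Nurminen interval stratified by country × maternal immunisation with CMH (sample-size) weights, for non-inferiority and superiority alike. Keep the unstratified interval as sensitivity.
2. **Sparse-cell rule, on counts only.** For example: if a cell has fewer than 5 subjects with a result in either group, merge that country's two maternal cells; if the country is still below 5 in either group, pool it with the next-smallest country. Determine the strata once and apply them identically to PPS and ES. Using PPS counts would serve, since the PPS is a subset of the ES. Fix the rule before unblinding and apply it mechanically afterwards, because counts by group need the treatment codes. State how a missing maternal status is classified.
3. **SAP 7.1.** State that the two factors are also the strata for the percentage analysis.
4. **SAP 3.3.** Add an entry if Protocol 9.4.3 is not itself amended.
5. **SAP 7.2.** At most a clarifying phrase: inference gives one overall estimate adjusted for the allocation factors.

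The cost is a few lines of text, a strata option and merging step in the code, and the documentation of a changed confirmatory analysis. No new data are needed. If the sponsor prefers the unstratified interval, one sentence in SAP 7.1 saying so would be enough.
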